6.4 Full Analysis Set

The full-analysis set (FAS) is those ITT subjects that have evaluable data for the endpoint.

6.5 Per-Protocol Set

The Per Protocol Set (PP) will include all randomized subjects in the FAS who did not have any major protocol violations. The DSMB or independent reviewer will identify major protocol violations, if any, prior to data lock and unblinding. If no subjects are excluded from the PP, the PP will not be required. The PP will be used for supporting analyses of efficacy data.

7. TIMING OF ANALYSES

Safety for the Roll-in cohort will be summarized when at least 2 weeks of follow-up is available on the last enrolled roll-in subject.

After the 30th, 60th, and 90th subject from the randomized cohort (active and control) is treated and followed for 7 days, the running safety report will be submitted to FDA. The report will be submitted within 30 days of treatment.

The interval safety report will include:

1. Cumulative frequency tables of all AE reported to date for the active patch, and all the AE reported to date for the sham patch, using the terminology in Table 9 in the investigational plan; and
2. A list of AEs in the recently completed 30-subject cohort, to include the device used (active or control), time to onset, time to resolution, intervention (including OTC product use), whether the AE was procedure- or device-related, and descriptive and photographic data.

Once all subjects complete 4 weeks of follow-up, the data will be summarized for evaluation of the endpoints. At this time, the sponsor will be unblinded to the treatment groups, but the investigators and subjects will remain blinded until study completion. Lastly, the data will be summarized when all subjects complete the study.

8. ASSESSMENT OF COMPARABILITY OF RANDOMIZED GROUPS AND EVALUATION FOR POOLING

8.1 Demographics / Baseline Characteristics and Protocol Administration

Patient disposition will be listed and summarized for the ITT and roll-in data sets by treatment group. Protocol deviations will be collected and summarized by randomized group in the ITT population and roll-in group.

Demographics (age, gender, race/ethnicity) and baseline characteristics (HDSS, GSP, Fitzpatrick skin type, and BMI) will be summarized by treatment group for ITT and roll-in groups.

The randomized groups will be compared at time of randomization for the important demographics and baseline characteristics specified. Should additional important baseline parameters be identified prior to the analysis, they will be evaluated in the same manner. Any of the variables that are significant at a two-sided $\alpha=0.05$ will be evaluated as covariates or strata variables in the primary effectiveness analysis or as an additional or supporting analysis to the primary effectiveness endpoint and if desired, secondary/observational endpoints as well. Continuous variables will be evaluated both as stratification variables by dichotomizing the subjects into two groups based on the median or other appropriate value and as a continuous variable in the statistical models. Logistic regression analysis may be used for the primary efficacy endpoint should it be desirable to evaluate multiple covariates simultaneously in a statistical model.

8.2 Treatment Characteristics

At a minimum, the duration of patch placement, pain level during treatment and cleaning will be summarized by randomized group for the ITT and roll-in population.

8.3 Evaluation for Pooling

Pooling of the investigational sites will be evaluated for the primary efficacy endpoint. Investigational centers with less than 10 randomized subjects will be combined for this purpose. The Breslow-Day test will be used to assess the treatment by site interaction and if statistically significant at $p<0.15$, an overall response rate will be evaluated at 4-weeks using CMH test stratified by site. If not statistically significant, the data will be pooled for analysis.

9. HANDLING OF MISSING DATA FOR THE PRIMARY EFFICACY ENDPOINT

A sensitivity analysis to the missing data in the ITT sample will be conducted for the primary efficacy endpoint. The sensitivity analysis will include a best case, worst case and tipping point analysis. The best case analysis will impute successes for subjects randomized to treatment with missing data and failures for subjects randomized to sham with missing data. The worst case analysis will impute failures for subjects randomized to treatment with missing data and success for subjects randomized to sham with missing data. The tipping point analysis completes the matrix of imputations possible between the best case and worst analysis to determine where statistical significance is maintained or lost. If the worst case analysis maintains statistical significance, the tipping point analysis is not necessary.

10. PRIMARY SAFETY ANALYSIS

Subjects Included in Analysis: All subjects in the Safety Population.

Endpoint(s): Local skin reactions and adverse events.

Hypothesis: A single hypothesis test associated with a specific safety endpoint is not being proposed for the primary safety outcome. Rather, the local skin reaction and adverse event profile in total will be reviewed for acceptability.

Primary Statistical Analysis: Number and percent of subjects affected by each DSMB classified event or reaction will be summarized. Subgroups of events/reactions will also be summarized and include but are not limited to serious events, those related to the treatment, and those that are both serious and related to the treatment. Events will additionally be summarized by DSMB determined severity and investigator reported time required for resolution. Treatment related AEs are defined by either a possible, probable, or highly probable relationship to the N-SWEAT Patch or possible, probable, or highly probable relationship to the N-SWEAT Procedure as adjudicated by the DSMB.

Lastly, adverse events will be summarized in subgroups defined by total time of treatment over both axilla, average and maximum pain throughout treatments. Subgroups will be defined by above and below the median for each treatment characteristic.

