17. Patients at risk for scarring, collagen vascular diseases, Hidradenitis suppurativa. Patients treated with isotretinoin may also experience severe scarring

TREATMENT APPROACH

Note: There is no difference in the treatment approach for the test vs. control groups. In the randomized cohort personnel are blinded to treatment assignments

INSPECTION	Final examination of the axilla to confirm freedom from any skin disease or irritation, including both visual and tactile assessment of any irregularities. Axilla must be free of abrasions, broken skin, or other conditions of concern. If both axillae do not meet this requirement, do not proceed with treatment.
IDENTIFICATION OF TREATMENT SITE	The target treatment area should be chosen by identifying a relatively flat area with the highest concentration of hair follicles; intended to maximize contact with the location of sweat production. For convenience, site may be marked.
PREP OF TREATMENT SITE	The subject's axilla (treatment site) will be cleaned with alcohol to ensure that no residual deodorant or other residue remains in the target treatment area. The area shall then be thoroughly dried.
PATCH APPLICATION	The clinician removes the release liner and applies the patch to the prepared and dried axillary area. The patch is held in place by the adhesive backing for the duration of the treatment, which is no longer than 3-minutes. Throughout the treatment period the clinician will observe the subject closely. If the subject experiences discomfort or pain that is significant (8 or greater pain level on a Wong-Baker FACES pain scale) the patch should be removed immediately even if it has been in place for less than 3 minutes.
POST TREATMENT	Immediately following patch removal, the treatment area will be cleansed thoroughly with water. A gauze pad soaked with water should be used to wipe the area a few times. This step should be repeated until the subject does not feel any residual effects. The patch should be placed into the disposal solution per instructions provided.
SECOND AXILLA	All the sequential steps above will be repeated for treatment of the second axilla in the same treatment visit.

RANDOMIZATION

RANDOMIZATION	Subjects in the randomized cohort will be randomized to one of two treatment groups in a 1:1 ratio to receive a single administration of N-SWEAT Patch or sham control patch in both axillae. The randomization will be stratified by HDSS 3 vs. 4 at baseline.

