4.3 Mechanism of Action

The N-SWEAT Patch is a non-invasive, topical patch designed to target and temporarily inactivate sweat glands using thermal energy, leading to reduced sweat production.

The N-SWEAT Patch is applied to the surface of dry, unabraded, intact skin by trained clinicians. The patch is activated by water released from sweat glands. When sweat (comprised of up to 99% water, Wilke et al. 2007) comes into contact with the patch, the sodium interacts with the water causing the patch to generate thermal energy. The amount and precise location of heat produced depends on the amount and location of sweat with which the patch comes into contact. In the absence of sweat (water), no thermal energy is generated.

The patch is applied for up to 3 minutes. Removal may occur prior to the 3-minute time point if the patient experiences pain or discomfort (as described in the Instructions for Use (IFU)).

The duration of the effect of the N-SWEAT patch is expected to be 6-8 weeks on average although early clinical data showed some patients maintained reduced sweat at 8-10 weeks. Duration time will be elucidated by this clinical study.

The N-SWEAT Patch is an Investigational Device and is limited by law for use only for subjects enrolled in an approved clinical study.

CANDESANT BIOMEDICAL	CLINICAL STUDY PROTOCOL SAHARA STUDY	Document #: CB-CLP-001 Revision: E
---------------------------------	---	---------------------------------------

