8.7.2 Patch Application

An overview of the patch application procedure is provided below; however, it is critical to reference the IFU provided for additional treatment and handling details.

Per the IFU, all personnel involved in the handling of the provided patch must have gloved hands at all times.

The patch will be placed on the target treatment area (as previously described). If the subject reports any pain or uncomfortable sensation at the time of patch placement; the patch should be immediately removed.

Upon placement of the patch, the timer shall be started. Every 30 seconds, the subject shall report their pain level on a score of 1 to 10. If the subject reports a pain level greater than 8 or shows a 8 or higher using the Wong-Baker FACES pain scale (**Figure 3**); the patch should be removed immediately regardless of the time that the patch has been in place.

Figure 3. Wong-Baker FACES® Pain Rating Scale

Wong-Baker FACES® Pain Rating Scale

If the timer reaches 3 minutes and the patch is still in place, it should be removed at the 3 minute mark. The actual treatment duration should be documented in the subject's study record. The procedure may be photographed or videotaped (provided the subject has consented to video/photography). The subject's identity will be concealed, and subject confidentiality will be maintained at all times.

NOTE: In the event of excessive exposure to the N-SWEAT patch or insufficient cleaning post treatment, an alkaline or thermal burn is possible. Acute burns are treated by flushing with water for 30 minutes followed by routine skin and wound care (Sander, 2011). Please have water and gauze available at all times when using the N-SWEAT patch.

Please refer to Appendix G for guidance on when to refer to a burn center.

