An analysis will also be performed using all available time points with complete follow-up at the time of the analysis. A generalized linear mixed model will be used to compare the proportion of subjects with HDSS of 1 or 2 between randomized groups over time on study. The dependent variable is HDSS of 1 or 2 (Y/N) with independent variables to include randomized group, follow-up time, baseline HDSS and two-way interaction terms. The covariance structure among the compound symmetric, auto-regressive and unstructured that provides the best model fit by the Schwarz BIC criterion will be used.

A hierarchical stepwise backward elimination technique will be used to reduce the model. The two-way interactions will be reviewed first, the two-way interaction with the largest p-value provided that p-value is greater than 0.05 will be removed from the model and the model refit and process repeated until only two-way interactions with p-values < 0.05 are retained. The main effects for any two-way interactions retained in the model must remain in the model as well as the randomized treatment. With that said, the main effects will be evaluated in the same manner as two-way interactions. This analysis will be repeated in the PP population as well.

Additional Statistical Analysis Subjects Randomized to Treatment: Logistic regression will be used to evaluate whether there is relationship between the total time that the patch was on both axilla and the primary efficacy endpoint as well as the average and maximum level of pain during treatment and the primary efficacy endpoint. The treatment characteristic will be evaluated as a continuous variable and a categorical variable dichotomized at the median value.

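### Patch time is capped at 3 minutes per axilla and cut short chiefly for pain, so a median split of total time (SAP 10 and 11.1) is likely to be uninformative and is confounded with pain

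*SAP*

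**What the plan says.** **The split.** SAP 10 states that "adverse events will be summarized in subgroups defined by total time of treatment over both axilla, average and maximum pain throughout treatments", and then: "Subgroups will be defined by above and below the median for each treatment characteristic". It gives no rule for values equal to the median and does not say whether the median is taken by arm or pooled. The analysis set is the safety population, which SAP 6.3 defines as both randomized arms plus the roll-in cohort. SAP 11.1 relates total patch time to the primary endpoint by logistic regression in subjects randomized to N-SWEAT: "The treatment characteristic will be evaluated as a continuous variable and a categorical variable dichotomized at the median value".

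**The cap.** The protocol synopsis says: "The patch is held in place by the adhesive backing for the duration of the treatment, which is no longer than 3-minutes". Protocol 8.7.2 adds: "If the timer reaches 3 minutes and the patch is still in place, it should be removed at the 3 minute mark".

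**Early removal.** Protocol 4.3 says: "Removal may occur prior to the 3-minute time point if the patient experiences pain or discomfort". Under Protocol 8.7.2, once a pain threshold is reached, "the patch should be removed immediately regardless of the time that the patch has been in place".

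**Recording.** Protocol 8.7.2 says: "The actual treatment duration should be documented in the subject's study record". It does not say to what resolution.

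**The concern.** A median split works for a variable that spreads out on both sides of its middle. Total patch time does not. It has a fixed ceiling, each patch is meant to reach that ceiling, and departures go one way only. The median may therefore equal the maximum, with no upper group, or it may separate people by a second or two of stopwatch handling.

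Time is also not set independently of the subject's reaction. A patch comes off early because the subject hurts, so short exposure partly marks how the skin responded. A table of adverse events by patch time could then be misread as an effect of exposure.

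This matters because Protocol 8.7.2 itself names an alkaline or thermal burn after excessive exposure as a hazard, and these are the planned analyses that relate patch time to adverse events and to HDSS response.

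**Working it through.** **Inputs**
- Cap: 3 minutes per axilla, two axillae, so 6:00 in total (Protocol synopsis and 8.7.2).
- Enrolment: up to 110 randomized 1:1 plus 10 roll-in subjects on N-SWEAT (SAP 2). The safety set is 55 + 10 = 65 N-SWEAT and 55 sham, 120 in all. The SAP 11.1 model has up to 55.
- q, the share of N-SWEAT subjects with early removal in at least one axilla, and s, the same for sham: not in the documents, so varied below.

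**1. The plan's own figures.** The plan states no number for the split. Only its sample size enters, as a denominator. The two-proportion formula (pooled variance, no continuity correction, two-sided 0.05, 80% power) gives 49 per arm for 85% vs 60% (plan: 50) and 45 for 73% vs 44% (plan: 45). Then 50 × 1.10 = 55 per arm, as stated.

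**2. When the upper group is empty.** Suppose full-term patches are recorded as exactly 3:00. Of N subjects, K have a total of 6:00, and nobody can exceed 6:00. The median equals 6:00 when K > N/2:
- N-SWEAT in the safety set: (65 + 1)/2 = 33 of 65.
- Randomized N-SWEAT: (55 + 1)/2 = 28 of 55.
- Pooled safety set: 120/2 + 1 = 61 of 120.

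**3. How likely that is.** With X ~ Binomial(N, q) early removals, nobody is above the median if X ≤ 32 (N = 65) or X ≤ 27 (N = 55). For the pooled set, total early removals must be at most 59.

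| Assumed q | N-SWEAT, 65 | Randomized N-SWEAT, 55 | Pooled 120, s = 0 | Pooled 120, s = 5% |
|---|---|---|---|---|
| 10% | 1.00 | 1.00 | 1.00 | 1.00 |
| 30% | 0.9996 | 0.999 | 1.00 | 1.00 |
| 40% | 0.95 | 0.93 | 1.00 | 1.00 |
| 45% | 0.79 | 0.77 | 1.00 | 1.00 |
| 50% | 0.50 | 0.50 | 1.00 | 1.00 |
| 60% | 0.05 | 0.07 | 1.00 | 1.00 |
| 80% | <0.001 | <0.001 | 0.99 | 0.91 |
| 90% | <0.001 | <0.001 | 0.64 | 0.27 |

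For a pooled median to leave the cap, q must reach about 60/65 = 92% if s = 0, (60 − 2.75)/65 = 88% if s = 5%, or (60 − 5.5)/65 = 84% if s = 10%. Within N-SWEAT the turning point is q of about 50%. With per-axilla rate r, q = 1 − (1 − r)² if axillae are independent, so q = 50% corresponds to r of about 29%; it corresponds to r = 50% if the axillae always agree.

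**4. If seconds are recorded.** Assume full-term times scatter around 3:00 with SD 2 s per axilla, and early removal shortens the total by 15 to 120 s. In simulation with 65 subjects:

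| Assumed q | Average median | Above median | Share of the lower group that are true early removals |
|---|---|---|---|
| 10% | 359.6 s | 43% | 23% |
| 30% | 358.3 s | 45% | 66% |

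The cut lies within 2 s of the 360 s ceiling.

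**5. What pooling could add.** As an illustration, take q = 30% and s = 0. The short-time group is 19.5 N-SWEAT subjects on average. The full-time group is 45.5 N-SWEAT + 55 sham = 100.5, of which 55/100.5 = 55% are sham. If events occur only on N-SWEAT, at a rate e unrelated to duration, the full-time rate is e × 45.5/100.5 = 0.45e. The short-time rate is then 1/0.45 = 2.2 times as high, with no effect of time at all.

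**The case against.** The strongest reply is that much of this is a missing tie rule. If totals pile up at exactly 6:00, splitting into below the median and at or above it gives early removal versus full time, which is the grouping wanted. SAP 3 refers to a table-shell document, not available here, that may hold such a convention. This has force when full-term times are recorded as exactly 3:00 and most subjects complete. It does not help if seconds are recorded, and it leaves the confounding unstated.

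Other points stand:
- The documents give no early-removal rate. Protocol 3.3 reports only that feasibility subjects found the pain acceptable.
- Recording the actual duration, with a timer running, may well mean seconds, and then people do fall above the median.
- The synopsis asks for safety summaries by treatment group as well as overall, so the median need not be pooled.
- SAP 11.1 also fits time as a continuous variable, and SAP 10 subgroups events by pain alongside time, so the link with pain would be partly visible.
- These are descriptive safety subgroups and a supporting model.

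A reader might infer that the upper group will be empty, or that 6 of 65 N-SWEAT completers suffice (61 − 55 = 6). The first needs a completion majority and exact 3:00 recording, neither of which the documents establish. The second also needs a pooled median and every sham subject completing. A reader might also infer that the table will show longer exposure as safer. Step 5 shows how that could arise under assumed rates; it is a risk, not a demonstrated result.

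**Conclusion.** The point holds in conditional form. The cap, the one-sided departures from it, the absence of a tie rule in SAP 10 and pain or discomfort as the only stated trigger for early removal are all in the documents. From these it follows that the median split of total time is likely to be uninformative:
- The upper group is empty if full-term patches are recorded as 3:00 and a majority in the split complete both applications.
- The cut falls largely in timer noise if seconds are recorded and early removals are a minority.
- If more than about half of N-SWEAT subjects have an early removal, a within-arm split has subjects on both sides, but it is still confounded with pain.

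The documents do not support saying that every planned analysis of exposure fails: the continuous-time model in SAP 11.1 has no empty cell, although it shares the confounding. The primary CMH test, the sample size and the success criterion are untouched. This is a correction worth making before the tables are run, not a threat to the trial's main conclusion.

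**What to change.** In SAP 10 and 11.1, for patch time only:

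1. Replace the median split with two groups, within N-SWEAT subjects: full planned time completed in both axillae, and removed early in at least one axilla. State the recording resolution and a tolerance, so that a second or two short of 3:00 is not counted as early.
2. Tabulate local skin reactions by axilla against that axilla's own duration.
3. Report the reason for each early removal.
4. State that the contrast is confounded with pain and is not to be read as an exposure effect.
5. Keep the continuous-time model, with the same caution, and keep the median split for pain scores.

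The sponsor should also reconcile the early-removal wordings in the protocol synopsis, 4.3 and 8.7.2. The synopsis uses a FACES score of 8 or more. Section 4.3 refers to pain or discomfort in general. Section 8.7.2 uses a reported score above 8 or a FACES score of 8 or more, and separately any pain at placement. These rules decide who enters the early-removal group.

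**Cost.** SAP and table-shell wording, and possibly one CRF field for the reason for removal; actual duration is already documented. The early-removal group may be small: at an assumed 10% rate, 0.10 × 65 = 6.5, so about 6 of 65 subjects.

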11. EFFICACY ANALYSIS

11.1 Primary Efficacy

The proportion of subjects with HDSS of 1 or 2 at 4-weeks in subjects randomized to treatment (p_T) will be higher than that in subjects randomized to sham (p_S).

Subjects Included in Analysis: All ITT subjects.

Endpoint(s): The proportion of subjects with HDSS of 1 or 2 at 4 weeks of follow-up.

Hypothesis:

H_0 : The proportion of subjects with HDSS of 1 or 2 at 4-weeks in subjects randomized to treatment (p_T) will be lower than or equal to that in subjects randomized to sham (p_S), $p_T \leq p_S$

H_a : The proportion of subjects with HDSS of 1 or 2 at 4-weeks in subjects randomized to treatment (p_T) will be greater than that in subjects randomized to sham (p_S), $p_T > p_S$

Sample Size Rationale: . The sample size and power calculations for the randomized cohort are based on the company's clinical trial data as well as on published data (Glaser et al., 2012). To account for substantial variability in the proportion of responders across various trials, multiple scenarios were considered.

Per definition of the primary endpoint a responder is a patient with HDSS values of 1 or 2 at 4-weeks post treatment. If proportions of responders in the treated vs. sham arms are 85% vs. 60%, respectively, then using PASS 2019, testing two proportions using the Mantel-Haenszel test, 50 patients per arm will be needed to detect the treatment difference with the 80% power at the 0.05 two-sided significance level. If proportions of responders in the

treated vs. sham arms are 73% vs. 44%, then 45 patients per arm will be needed. The evaluable sample size of 50 patients per arm was chosen

Primary Statistical Analysis: The proportion of patients with HDSS of 1 or 2 at 4 weeks post-treatment will be compared between treatment vs. sham using the Cochran-Mantel-Haenszel (CMH) test stratified by baseline HDSS value of 3 vs. 4 in the FAS population. Statistical significance is achieved with two-sided p-value <0.05 equivalent to one-sided p-value < 0.025.

Additional Statistical Analysis: Additional analyses include those summarized in **Section 8.3** Evaluation for Pooling of Data and **Section 9** Handling of Missing Data for the Primary Efficacy Endpoint. The primary statistical analysis will be completed in the PP population as well.

An analysis will also be performed using all available time points with complete follow-up at the time of the analysis. A generalized linear mixed model will be used to compare the proportion of subjects with HDSS of 1 or 2 between randomized groups over time on study. The dependent variable is HDSS of 1 or 2 (Y/N) with independent variables to include randomized group, follow-up time, baseline HDSS and two-way interaction terms. The covariance structure among the compound symmetric, auto-regressive and unstructured that provides the best model fit by the Schwarz BIC criterion will be used.

A hierarchical stepwise backward elimination technique will be used to reduce the model. The two-way interactions will be reviewed first, the two-way interaction with the largest p-value provided that p-value is greater than 0.05 will be removed from the model and the model refit and process repeated until only two-way interactions with p-values < 0.05 are retained. The main effects for any two-way interactions retained in the model must remain in the model as well as the randomized treatment. With that said, the main effects will be evaluated in the same manner as two-way interactions. This analysis will be repeated in the PP population as well.

Additional Statistical Analysis Subjects Randomized to Treatment: Logistic regression will be used to evaluate whether there is relationship between the total time that the patch was on both axilla and the primary efficacy endpoint as well as the average and maximum level of pain during treatment and the primary efficacy endpoint. The treatment characteristic will be evaluated as a continuous variable and a categorical variable dichotomized at the median value.

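### The within-arm logistic models of patch time and pain against response name no baseline covariate, so differences in baseline HDSS can show up as an exposure-response association

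*SAP*

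**What the plan says.** The last paragraph of SAP 11.1, for subjects randomised to treatment, states: "Logistic regression will be used to evaluate whether there is relationship between the total time that the patch was on both axilla" and the primary endpoint. Average and maximum pain are treated in the same way. On the form of the predictor it says: "The treatment characteristic will be evaluated as a continuous variable and a categorical variable dichotomized at the median value". It names no other term. The protocol's primary efficacy section (9.10.1) has no such analysis, so this paragraph is its only specification.

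The two other primary-endpoint analyses in SAP 11.1 do use baseline HDSS. The primary test is a "Cochran-Mantel-Haenszel (CMH) test stratified by baseline HDSS value of 3 vs. 4 in the FAS population", and the over-time model has "independent variables to include randomized group, follow-up time, baseline HDSS and two-way interaction terms". SAP 8.1 provides for covariates, but only for variables that differ between the randomised groups. It does not reach a model fitted within one arm.

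Three further statements matter:
- **Endpoint:** "a responder is a patient with HDSS values of 1 or 2 at 4-weeks post treatment" (SAP 11.1).
- **Heat:** "The amount and precise location of heat produced depends on the amount and location of sweat with which the patch comes into contact" (Protocol 4.3).
- **Removal:** when pain reaches the trigger, "the patch should be removed immediately regardless of the time that the patch has been in place" (Protocol 8.7.2).

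**The concern.** Within one arm, pain and wear time arise from the subject and the procedure. Anything that affects both the exposure and the response will confound the association.

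Baseline HDSS is tied to the response by the endpoint definition, since an HDSS 4 subject has further to fall. It may also be tied to the exposure. If subjects with worse HDSS sweat more, the mechanism in the protocol leads from sweat to heat, from heat to pain, and from pain to early removal.

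These models are the SAP's only analyses of whether wear time or pain goes with efficacy. An unadjusted result could suggest that pain or early removal accompanies poorer response when the cause is starting severity. The point concerns the continuous models as much as the median split, so it is separate from the choice of cut-point.

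There is also a matter of timing. Under SAP 7 the sponsor is unblinded at the 4-week analysis. Covariates not named beforehand could be chosen with the results in view.

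**Working it through.** **1. The plan's own figures.** The documents give no figure for these models, but the sample size rationale supplies the arm size and response rates. With n = [1.960·√(2p̄q̄) + 0.842·√(p₁q₁ + p₂q₂)]² / (p₁ − p₂)²:
- 85% vs 60%: (1.238 + 0.510)² / 0.0625 = 48.9, so 49 per arm (stated: 50).
- 73% vs 44%: (1.366 + 0.560)² / 0.0841 = 44.1, so 45 per arm (stated: 45).

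These reproduce, and no numerical error is at issue. The inputs carried forward are 55 randomised per arm and a treated response of 73% to 85%.

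**2. Non-responders available.** 55 × 0.15 = 8.3 and 55 × 0.27 = 14.9, so about 8 to 15. With exposure and HDSS in the model that is about 4 to 7 per parameter. Adding GSP leaves about 3 to 5.

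**3. Simulation of the pain model.** There are 55 N-SWEAT subjects. Pain is 4 + gap × (HDSS 4) + 2 × N(0,1). Response depends on HDSS only, so the true pain effect is nil. The assumptions, none of them in the documents, are a 30% share of HDSS 4, a pain SD of 2, the pain gap, and the split of response between HDSS 3 and 4.

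The overall rates implied by the splits are:
- 0.7 × 88 + 0.3 × 78 = 85%
- 0.7 × 90 + 0.3 × 60 = 81%
- 0.7 × 85 + 0.3 × 45 = 73%

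The corresponding HDSS odds ratios are:
- (0.78/0.22)/(0.88/0.12) = 0.48
- (0.60/0.40)/(0.90/0.10) = 0.17
- (0.45/0.55)/(0.85/0.15) = 0.14

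| Response HDSS 3 / 4 | Pain gap (points) | Unadjusted median OR per SD of pain | Falsely significant |
|---|---|---|---|
| 88% / 78% | 1 | 0.92 | 4% |
| 90% / 60% | 0.5 | 0.89 | 6% |
| 90% / 60% | 1 | 0.81 | 7% |
| 90% / 60% | 2 | 0.69 | 16% |
| 85% / 45% | 1 | 0.80 | 9% |
| 85% / 45% | 1.5 | 0.74 | 14% |

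Repeat runs differ by about 0.01 to 0.02 in the OR and about one percentage point in the rate. With baseline HDSS in the model, the median OR is about 1.0 and 3% to 5% are significant.

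**4. A second set of assumptions.** Here n = 50, 40% are HDSS 4 and overall response is 73%.
- HDSS OR 0.5 and a 0.5 SD shift in pain: unadjusted OR 0.91, 4% significant.
- HDSS OR 0.25 and 0.8 SD: 0.76, 10%.
- An extreme case, HDSS OR 0.1 and 1.2 SD: 0.58, 34%.
- No shift in exposure, or HDSS OR of 1: about 1.0, about 4%.
- With HDSS in the model: about 1.0, 3% to 6%.

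**5. Patch time.** In a large-sample model, baseline sweat reaches response only through its correlation with HDSS. The spurious OR for full time versus early removal is about 1.0 at correlation 0, 1.02 to 1.11 at 0.2, 1.06 to 1.26 at 0.4, and 1.07 to 1.41 at 0.6. These correlations are also assumed.

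**The case against.** The strongest reply is that only one side of the confounding is documented for each variable. HDSS is tied to response by definition, but no data link it to pain or wear time. Sweat is tied to heat by mechanism, but nothing links baseline GSP to HDSS response. Protocol 3.3 itself doubts that GSP reflects the level of disease, and eligibility confines GSP to roughly 50 to 300 mg/5 min per axilla. A reader might infer that baseline HDSS and sweat drive both sides, so that severity is bound to appear as an exposure effect. The documents do not support that. The effect is possible, and its size rests on assumptions. The pH sub-study (SAP 13) sets a minimum number of HDSS 4 subjects and reports pH by HDSS, which suggests the sponsor thought HDSS relevant to the patch reaction. That is a hint and not data.

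The analysis is also supportive. SAP 11.2.1 keeps such results out of additional claims, and SAP 12 already summarises the primary endpoint by baseline HDSS, so a gradient in response would be visible. Both points stand and limit the importance of this one. They do not supply the missing covariate.

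Finally, adjusting for GSP is doubtful. Sweat activates the patch and so belongs to the delivered-dose pathway. Conditioning on it changes the question and may remove a real effect. This objection stands.

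**Conclusion.** The gap holds as a minor one. These within-arm models omit the stratification factor that both neighbouring analyses use, and no other section supplies it. Over the main range of assumed links, the unadjusted OR per SD of pain is about 0.92 to 0.69 with 4% to 16% false positives. At the weak end the test keeps its nominal level and only the estimate is shifted. There is no bias if HDSS is unrelated to either exposure or response. For wear time the likely distortion is smaller unless sweat and HDSS are well correlated.

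A reader might also infer that the trial's efficacy conclusion is at risk. It is not: neither the primary CMH test nor any step of the secondary hierarchy uses these models.

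**What to change.** In the last paragraph of SAP 11.1:
- Include baseline HDSS (3 vs 4) in each logistic model: total patch time, average pain and maximum pain.
- Fit by Firth or exact conditional logistic regression, given the 8 to 15 non-responders expected.
- Report the unadjusted version as secondary.
- Label all of these models descriptive.
- Treat a further model with baseline total GSP as at most an optional sensitivity analysis, with a note that it addresses a different question.

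The cost is a few lines of SAP wording, as baseline HDSS is already collected. Intervals will be somewhat wider. Penalised or exact methods deal with sparse data and separation but add no information.
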